1.0 SYNOPSIS

Title:	Usefulness of Unipolar and Bipolar Electrograms in Predicting Successful Ablation Site during Idiopathic Outflow Tract Ventricular Arrhythmia Ablation
Acronym:	EGM Analysis in Idiopathic OTVA
Purpose:	Investigate the value of unipolar and bipolar electrograms (EGM) for predicting the successful ablation site for idiopathic outflow tract ventricular arrhythmia (OTVA)
Objectives:	Primary Objective: Evaluate the predictive value of using reversed polarity in adjacent bipolar EGMs (bi-RP method) and unipolar EGM with QS morphology (uni-QS method) for identifying successful ablation site
	Secondary Objective: Evaluate the feasibility of enhancing uni-QS method’s performance by using its morphology characteristics such as descending slope and symmetry
Endpoints:	Primary Endpoint: Predictive values of the bi-RP method and uni-QS method for successful ablation Secondary Endpoint: Predictive value of a new method by combining bi-RP and uni-QS for successful ablation.
Design:	The study is an acute, non-randomized, feasibility study in Fuwai Hospital, China.
Devices used:	Any commercially available SJM quadripolar RF ablation catheters in China.
Study Population	Approximately 20 patients meeting the specific criteria.
Inclusion/Exclusion Criteria	Inclusion Criteria: - Patients scheduled to undergo ablation for idiopathic OTVA - Have the ability to provide informed consent for study participation. Exclusion Criteria - Be currently participating in any other investigational study - Be less than 18 years of age - Be pregnant - Has any other conditions that are not suitable for catheter ablation (including but are not limited to active whole-body infection or sepsis, coagulation or hemorrhage disorder history)
Data Collection	Data will be collected at: Enrollment and OTVA ablation visit.

CIP

1.1 Study Flow Chart

[figure not shown]

Figure 1: Study flow from enrollment to end of protocol

2.0 BACKGROUND AND JUSTIFICATION FOR CLINICAL STUDY

Currently, the first-line therapy for symptomatic Ventricular Arrhythmia (VA) patients is still antiarrhythmic drugs¹. Unfortunately, drug therapy is not always effective and can be hindered by side effects¹⁻³. As an alternative, Radiofrequency Catheter Ablation (RFCA) has been shown to be highly effective in treating focal idiopathic VAs in the outflow tract (OT), with acute success rates greater than 80%^{1,4-6}. Although RFCA is generally considered a safe procedure, serious complications may still occur^{1,7-8}. Therefore, it is important to minimize the number of lesions while achieving an effective treatment.

The classic strategy to guide RFCA is based on local activation time (LAT) map and the presence of a QS morphology in the unipolar electrograms (uni-QS)⁹⁻¹². However, the actual LAT at the successful ablation site may vary a lot among patients, and the area demonstrating a unipolar QS morphology may be larger than the focal source⁹⁻¹². In practice, these factors may greatly affect the efficiency of the physicians to locate the focal source and cause unnecessary ablation lesions. Thus, more specific criteria are needed to help guide the search for successful ablation site.

The presence of reverse polarity in adjacent bipolar electrograms (bi-RP) has been demonstrated in pulmonary vein isolation procedure using circular catheter based on the hypothesis that the excitation wavefront propagates radially from the breakthrough site in the pulmonary vein¹⁴. A similar approach using the reversal initial deflection of adjacent bipolar electrograms has been demonstrated in patients with accessory pathways and focal atrial tachycardia¹⁵. Lately, Carine et al., in a retrospective analysis, showed that a method combining the use of LAT and bi-RP phenomenon in focal right ventricular outflow tract (RVOT) arrhythmias could yield a higher specificity for identifying successful ablation sites than the conventional LAT plus unipolar QS morphology method¹⁶.

The proposed study aims to evaluate the predictive value of bi-RP and uni-QS for identifying successful ablation site. It will also evaluate the feasibility to enhance uni-QS method's performance by using uni-QS and its morphology characteristics such as descending slope and symmetry.

CIP

3.0 RISKS AND BENEFITS OF THE CLINICAL STUDY

3.1 Description of subject population

The inclusion/exclusion criteria for participation in this study is specified in section 4.5. This study will attempt to recruit consecutive subjects who meet all inclusion criteria and does not meet any exclusion criteria for study enrollment. A signed Informed Consent Form (ICF) for study participation must be obtained by the principal investigator (PI) or designated personnel prior to subject enrollment.

3.2 Anticipated clinical benefits

There is no direct benefit to the studied patient because we simply collect electrograms during the ablation procedure. However, findings from this study may help physicians to develop more efficient ablation strategy and potentially benefit future patients.

3.3 Anticipated adverse events and adverse device effects

There are no adverse events associated with the additional data collection for this study. Possible adverse events (in alphabetical order) associated with the standard RFCA include but are not limited to the following:

- Allergic reactions to contrast media (agents)
- Arrest (cardio)
- Arrest (respiratory)
- Arrhythmias
- Air embolism
- Bleeding (non-hematoma)
- Cardiac perforation
- Cardiac tamponade
- Damage to the conduction system
- Damage to the coronary arteries
- Death
- Endocarditis
- Groin hematoma
- Heart failure
- Hemothorax
- Myocardial ischemia
- Myocardial Infarction
- Phrenic nerve injury
- Periprocedural death
- Stroke or transient ischemic attack
- Thromboembolism
- Valve injury
- Vascular injury

3.4 Residual risks associated with the study, as identified in the risk analysis report

The risks in this study are similar to the risks associated with standard RF ablation procedure for OTVA.

CIP

3.5 Risks associated with participation in the clinical study

Participation in this study does not provide additional risk to the subjects who will nevertheless undergo RF ablation for OTVA. No additional device or catheter will be inserted during the procedure, nor should the procedure time be lengthened due to participation in this study. As with any interventional procedure, participation in this study has risks and complications that are associated or anticipated with percutaneous vascular access and catheter ablation.

3.6 Risk-to-benefit rationale

There is no additional risk more than the risks associated with standard RF ablation procedure for OTVA. Findings from this study may help physicians to develop more efficient ablation strategy and potentially benefit future patients.

4.0 STUDY DESIGN

4.1 Purpose

The purpose of this clinical study is to investigate the value of unipolar and bipolar EGM for predicting the successful ablation site for idiopathic OTVA.

4.2 Study Design and Scope

The study is an acute, non-randomized, feasibility study.

- Approximately 20 subjects meeting the inclusion criteria will be enrolled in this study
- The estimated time to enroll the required patients is 6 months
- The study will be conducted in one medical center, the Fuwai Hospital in Beijing, China.

Number of subjects required to be included in the study

Approximately 20 subjects meeting the inclusion criteria will be enrolled in this study.

Estimated time needed to enroll this subject population

The estimated time to enroll this subject population is 6 months. The study may continue up to 12 months, dependent on the rate of enrollment and the regulatory timeline.

4.3 Objectives

Primary Objective

Evaluate the predictive value of using reversed polarity in adjacent bipolar EGMs (bi-RP method) and unipolar EGM with QS morphology (uni-QS method) for identifying successful ablation site

Secondary Objective

Evaluate the feasibility of enhancing uni-QS method's performance by using its morphology characteristics such as descending slope and symmetry.

4.4 Endpoints

Primary Endpoint

Predictive values of the bi-RP method and uni-QS method for successful ablation

CIP

Secondary Endpoint

Predictive value of a new method by combining bi-RP and uni-QS for successful ablation.

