6.4 Ablation Procedure Visit

In case the patient's VA is not present and cannot be induced before the ablation procedure, the ablation should not be performed according to the 2009 EHRA/HRS Expert Consensus on Catheter Ablation of Ventricular Arrhythmias¹. The following actions will be taken:

- Inform the subject about the withdrawal.
- Complete the Withdrawal CRF. The form must be authorized / approved by the principal or delegated investigator

The ablation procedure will be performed according to the Fuwai hospital's standard practice. During the ablation procedure, any clinical adverse events or protocol deviations are to be noted on the appropriate forms. The following information will be collected at the ablation procedure visit:

- Date of procedure

CIP

- The unipolar EGM, the bipolar EGM pairs as defined below, and the 12-lead surface ECG.
- Nonsuccessful and successful ablation sites tagged on the map.
- Acute success rate
- Indicate model and number of mapping and ablation catheters used in the procedure
- Adverse Events, Death, and/or Protocol Deviation notification (if applicable)

Mapping and EGM Recording

A quadripolar ablation catheter will be used to map the target site. Specifically, the unipolar EGM is recorded from the distal electrode (M1) of the mapping catheter and filtered at 0.5~100Hz. The bipolar EGMs are recorded from the distal (M1-M2), mid (M2-M3), and proximal (M3-M4) electrode pairs of the mapping catheter, respectively, and filtered at 30~500Hz. LAT is measured using the distal electrode pair and is defined as the interval between the initial sharp peak of the EGM and the onset of the VA QRS. The presence of the bi-RP is evaluated between the distal and mid electrode pairs and is defined as a rapid simultaneous deflection in the opposite direction of the initial part of the bipolar EGM occurring before the onset of the VA QRS. All the unipolar EGM, bipolar EGMs, and the 12-lead surface ECG will be displayed on the monitor for the physician’s reference and stored on the electrophysiology recording system and on the Ensite Velocity mapping system for off-line analysis. To guarantee accurate electroanatomic activation mapping and to avoid annotation of catheter-induced premature ventricular contractions (PVCs), the VA QRS morphology of each acquired mapping point will be compared to a 12-lead QRS template of the clinical arrhythmia.

Ablation

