11.0 STATISTICAL CONSIDERATIONS

11.1 Statistical design, hypotheses, method and analytical procedures

This study is an acute, prospective, non-randomized, feasibility study.

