11.2 Sample size

This feasibility study is expected to be conducted in the Fuwai Hospital, Beijing, China. It is designed to investigate 20 subjects meeting the inclusion criteria. As a feasibility study, there is no statistical-based sample size. Because this study does not require follow-up visits, attrition (i.e. incomplete data set due to deviation from protocol) is anticipated to be low - in approximately 5% of patients. In case of substantial drop-out rate (more than 10%), an increase in population will be conducted by amendment.

CIP

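### The slope and symmetry criteria for enhancing uni-QS are not fixed in advance and no validation step is planned, so a rule chosen and scored on the same 20 or so patients will be biased upward.

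*Combined protocol and SAP*

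**What the plan says.** Section 4.3 sets the secondary objective: "Evaluate the feasibility of enhancing uni-QS method's performance by using its morphology characteristics such as descending slope and symmetry". The words before the two examples leave the feature list open. Nothing in the plan says how slope or symmetry is measured, which direction counts as favourable, or where a cut-off lies. By contrast, section 6.4 defines LAT and bi-RP in operational terms.

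Section 4.4 sets the secondary endpoint: "Predictive value of a new method by combining bi-RP and uni-QS for successful ablation". Slope and symmetry are absent, and no rule for the combination is given.

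Section 11.1, headed as covering design, hypotheses and methods, is a single sentence: "This study is an acute, prospective, non-randomized, feasibility study". Section 11 has no split into derivation and test data, no cross-validation or bootstrap correction, no external data set and no step that locks the criteria. Electrograms are "stored on the electrophysiology recording system and on the Ensite Velocity mapping system for off-line analysis", and no masking to site outcome is stated.

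On size, section 4.2 says "Approximately 20 subjects meeting the inclusion criteria will be enrolled in this study", and section 11.2 says "As a feasibility study, there is no statistical-based sample size". The case report forms are under separate cover; the plan does not point to them for these definitions.

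**The concern.** Slope is a continuous quantity, and so is symmetry unless it is graded by eye. To call a site positive or negative, an analyst must pick a feature, a direction and a cut-off. If those choices are made by looking at which sites succeeded, and the rule is then scored on the same sites, part of its apparent accuracy is fit to chance. Plain uni-QS is the presence or absence of a QS complex and has no tuned cut-off, so a comparison between the two leans towards enhancement.

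At stake is the answer to the secondary question, and with it the choice of criteria to carry into a later study. Section 15.0 commits to submitting the results for publication, and section 9.0 allows for transfer of the data in support of a market-approval application.

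**Working it through.** **No figure to reproduce.** The 20 subjects have no alpha, power or effect size behind them. The check is a simulation of what happens if the open choices are made on the study data.

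**Inputs from the plan.** 20 subjects and about 5% attrition (section 11.2); withdrawn subjects are left out of the analysis (section 11.4). Evaluable patients: 20 × 0.95 = 19. Each ablated site is tagged successful or nonsuccessful (section 6.4, Ablation).

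**Assumptions, because the plan is silent.** One successful and k nonsuccessful sites per patient, with k = 1, 3 or 5. Two independent normally distributed features unrelated to outcome. Both directions are searched, and the cut-off maximises the Youden index J = sensitivity + specificity − 1. For an uninformative rule the true J is 0 and the true PPV is 1/(1 + k).

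**Step 1: stand-alone rule, chosen and scored on the same 19 patients.**

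| k | Apparent J (true 0) | Apparent PPV | True PPV | Leave-one-patient-out PPV |
|---|---|---|---|---|
| 1 | 0.30 | 69% | 1/2 = 50% | 49% |
| 3 | 0.25 | 39% | 1/4 = 25% | 27% |
| 5 | 0.24 | 27% | 1/6 = 17% | 17% |

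For the last column, feature, direction and cut-off are chosen on the other patients, the left-out patient's sites are classified, and the results are pooled. This removes nearly all of the optimism.

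**Step 2: false gain over plain uni-QS.** An enhancement acts on sites that are already uni-QS positive, so the relevant quantity is J(uni-QS and feature beyond cut-off) − J(uni-QS). The plan gives no accuracy for uni-QS, so three assumed settings are shown.

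| Assumed uni-QS sensitivity, false-positive rate | k = 1 | k = 3 | k = 5 |
|---|---|---|---|
| 0.90, 0.20 | 0.04 | 0.03 | 0.03 |
| 0.90, 0.40 | 0.08 | 0.06 | 0.06 |
| 0.95, 0.60 | 0.14 | 0.11 | 0.10 |

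The true gain is not positive in any cell. Depending on the setting, the best cut-off gave exactly zero gain in 0 to about 40% of simulated studies.

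**Step 3: the endpoint as section 4.4 words it.** With two uninformative binary markers (each assumed positive at half of the sites, 20 patients), choosing the better of AND and OR gives a mean apparent J of 0.05 to 0.06 for 1 to 9 nonsuccessful sites per patient.

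**Step 4: sensitivity to the search.** This step uses 20 patients, a rule requiring both features, and 1 to 9 nonsuccessful sites per patient.

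- Direction free, fine grid of cut-offs: mean apparent J 0.27 to 0.35.
- Direction fixed, fine grid: 0.19 to 0.25.
- Direction fixed, three candidate cut-offs per feature: 0.10 to 0.14.
- Cut-offs fixed in advance: 0.00.
- Any data-chosen rule applied to fresh data: about 0.00.

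More nonsuccessful sites reduce the optimism only a little, because the number of successful sites stays near 20.

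**The case against.** The strongest reply has four parts.

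- **Feasibility.** The study is labelled a feasibility study, states no hypothesis and does not claim a validated rule. Deriving a rule is a legitimate aim here. This stands as a reason to label the result exploratory, but the label does not remove the bias from the estimate.
- **The plan does not say that cut-offs will be tuned on its own data.** This stands. Tuning is inferred from the absence of any pre-set criteria and of any second data set. A reader might infer that the plan prescribes scoring a rule on its own derivation data; the text does not go that far.
- **Section 4.4 combines two binary criteria, with no continuous cut-off to tune.** This also stands. On that reading the optimism is only about 0.05. The larger problem comes from the objective in section 4.3, and the two sections need reconciling.
- **The stand-alone figures overstate the harm.** Correct. A reader might take 0.24 to 0.30 as the size of the false enhancement, or conclude that the study could never return a finding of no enhancement. Step 2 supports neither: the false gain is smaller, and in some settings it is often exactly zero.

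The remedy also has a limit. The leave-one-patient-out estimate is close to unbiased but noisy: in repeated runs its PPV had a standard deviation of about 0.17 to 0.19, 0.11 to 0.12 and 0.07 to 0.09 for k = 1, 3 and 5.

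**Conclusion.** The point holds as a conditional one. The plan fixes no criteria for slope or symmetry, leaves the feature list open, has no validation step, and describes no data beyond the same 20 or so patients. Its secondary objective and endpoint also describe different methods. If cut-offs are chosen and scored on those patients, the bias is upward. For uninformative features under a free search, the apparent Youden index is about 0.24 to 0.30 for a stand-alone rule, and the false gain over plain uni-QS is about 0.03 to 0.14. Choosing only between AND and OR of bi-RP and uni-QS gives about 0.05. These sizes rest on assumed numbers of sites per patient, an assumed search rule and assumed uni-QS accuracy; a narrower search gives less. The direction of the bias does not depend on those assumptions. The issue should be corrected before analysis, but it does not undermine the study as a feasibility exercise.

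**What to change.** In sections 4.3, 4.4 and 11.1:

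1. Make the secondary objective and the secondary endpoint describe the same method or methods.
2. Limit the candidates to descending slope, symmetry and the bi-RP/uni-QS combination, and state how each is measured.
3. Either fix definitions, directions, cut-offs and the combination rule before analysis, or score any rule derived from the study data by leave-one-patient-out cross-validation or bootstrap optimism correction, with the patient as the unit and the whole selection repeated each time.
4. Report the corrected gain over plain uni-QS with a patient-level bootstrap interval. Show the same-data figure only as apparent, and label the result exploratory.

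The cost is a few lines of text and some code on data already being collected, with no extra patients or procedures. The reported value will be lower than the apparent one, and with about 20 successful sites its interval will be wide.

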4.5 Inclusion and Exclusion Criteria

A subject, who meets all of the inclusion criteria, and none of the exclusion criteria, is eligible to participate in this study.

All subjects enrolled in the clinical study (including those withdrawn from the clinical study or lost to follow-up) will be accounted for and documented, assigning an identification code linked to their names, alternative identification or contact information.

This log will be kept up to date throughout the clinical study by the principal investigator or his/her authorized designee. To ensure subject privacy and confidentiality of data this log must be maintained throughout the clinical study at the clinical site.

To participate in this clinical subject, the subject must meet all of the following inclusion criteria:

Inclusion Criteria

Subjects are eligible for clinical study participation if they meet all of the following inclusion criteria:

- Patients scheduled to undergo ablation for idiopathic OTVA
- Have the ability to provide informed consent for study participation.

Exclusion Criteria

Patients will be excluded from the study if they meet any of the following exclusion criteria:

- Be currently participating in any other investigational studies
- Be less than 18 years of age
- Be pregnant
- Has any other conditions that are not suitable for catheter ablation (including but are not limited to active whole-body infection or sepsis, coagulation or hemorrhage disorder history)

4.6 Subject Population

Subject Screening

All subjects presenting at the investigational site can be screened by a member of the investigational team previously trained on the CIP and delegated to do so.

Subjects who do not meet the inclusion/exclusion criteria will not be eligible to participate in this study.

Subjects meeting the inclusion/exclusion criteria will be fully informed about the study and asked to participate in the study. In case the subject agrees, a duly signed and dated ICF will be obtained.

Point of Enrollment

Subjects are considered enrolled in the study from the moment the subject has provided written ICF. (Refer to section 4.7 for the Informed Consent Process).

CIP

4.7 Informed Consent Process

General process

Prior to enrolling in the clinical study and conducting study-specific procedures, all subjects will be consented, as required by applicable regulations and the center’s IRB/EC. Informed consent must be obtained from each subject prior to any study related procedures. The consent form must be signed and dated by the subject and by the person obtaining the consent.

The principal investigator or his/her authorized designee will conduct the Informed Consent Process. This process will include a verbal discussion with the subject on all aspects of the clinical study that are relevant to the subject’s decision to participate in the clinical study.

The subject shall be provided with the informed consent form that is written in a language that is understandable to the subject and has been approved by the center’s IRB/EC. Failure to obtain informed consent from a subject prior to study enrollment should be reported to St. Jude Medical within 5 working days and to the reviewing center’s IRB/EC consistent with the center’s IRB/EC reporting requirements.

5.0 DEVICE UNDER INVESTIGATION

5.1 Device Description

All the devices and systems (including software) used in this study are commercially approved in China. Including the following items:

- Any standard fluoroscopy equipment used in the Fuwai Hospital
- Any standard EP recording systems used in the Fuwai Hospital
- Any SJM quadripolar ablation catheters (e.g. the Safire Ablation Catheter)
- Any SJM ablation therapy hardware (e.g. the 1500T series Cardiac Ablation Generator, Cool Point Irrigation Pump)
- The SJM Ensite Velocity Cardiac Mapping System

